Screening questions that warrant follow up if the participant answers "yes":

- Have you been diagnosed with a methamphetamine use disorder? (follow up- providers to determine if participant should have a methamphetamine use diagnosis, if not currently diagnosed)
- Are you claustrophobic or afraid of small, closed-in spaces? (follow-up- participant needs to confirm that they can handle being in an MRI machine through additional questions)
- Do you have a problem with loud noises? (follow-up- participant needs to confirm that the noises from the MRI are not too loud through additional questions)
- Have you ever had a neurosurgical procedure? (follow up- type of procedure matters)
- Have you been diagnosed with another neurological disorder? (follow-up- type of disorder matters)
- Are you able to make it to all visits for this study without assistance?
Additional information: This involves a baseline visit, then visits five days a week for two weeks and three days a week for two more weeks. The visits need to take place Monday through Friday, but we can start most any day depending on what's convenient for you. There will also be follow-up visits that can be completed by phone or in person one month and two months after the other visits are completed.
 - If not, Please explain any additional services you may need to get to and from study appointments, (i.e. transportation)

Randomization

The randomization scheme was block randomization stratified by study site, with block sizes of 4 and a 1:1 ratio, designed to ensure approximate balance in the number of subjects. Subjects are randomized to receive stimulation at the DLPFC or MPFC first, although both groups receive stimulation at both sites at each visit. The subject is assigned to a group at the first TMS treatment visit.

Intervention

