Assessment visit 1 will take place prior to TMS treatment. Information will be collected on demographics and a history of substance use and medical conditions. Subjects will be screened using the MINI International Neuropsychiatric Interview to ensure they do not have mental health conditions that should lead to exclusion. This may be conducted remotely by a psychiatrist investigator using a HIPAA compliant Zoom meeting if a psychiatrist is not available to perform the MINI on-site. The subject will complete all assessment surveys. They will also complete several psychological tests, including a Flanker task administered with an iPad, and a digitally administered delay discounting task. They will also submit a urine drug screen if there is not a recent result on file in their EHR, or one is not known to be planned for that day. Then they will complete fMRI imaging. This visit should take 3-4 hours. If the subject elects to participate in the optional EEG and timing task, this will add about an hour to this visit. If they elect to participate in this optional EEG and task, investigators will adhere electroencephalogram (EEG) leads to their scalp and then have them perform 2 blocks of the interval timing task where they estimate the passage of a specified (3 or 12 second) passage of time (~22min - 11 min blocks). The beginning of the trial is indicated by the presentation of either a 3 or a 12 on the computer screen which also indicates the duration of time the subject should estimate. During performance, we will collect electroencephalographic data from patients which will be analyzed offline. Within a week of this visit, the subject will begin TMS treatment. TMS treatment could start as early as the same day if the subject prefers and the schedule allows.

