This is a pilot study without an untreated control group so will not be able to establish that the treatment is causal in improving outcomes. The overarching goal is to evaluate the ability to recruit and retain subjects, establish safety of the intervention in this population, evaluate target engagement of TMS using fMRI, and to determine the extent to which patient symptoms and substance use appear to improve during participation in treatment. We anticipate approximately 20 subjects, which should be adequate to statistically detect clinically meaningful changes in symptoms and other outcome measures, depending on attrition. We will randomize order of treatments to gather preliminary data on any differences, but do not anticipate power to detect significant differences in effect by order of treatment with this sample size.

Outcomes

Primary outcomes:

1. Retention in the Study: Measured from Baseline to 12 weeks
2. Retention in Psychosocial Treatment: Measured from Baseline to 18 days (self-reported)

Secondary outcomes (used all available data points as specified in figure 2):

1. Functional Connectivity of the Dorsolateral Prefrontal Cortex and Anterior Insula—change from baseline to 4 weeks. Measured by correlation of region activity over MRI time series data, averaged for left and right hemisphere.
2. Functional Connectivity Dorsolateral Prefrontal Cortex and Anterior Cingulate Cortex—change from baseline to 4 weeks. Measured by correlation of region activity over MRI time series data, averaged for left and right hemisphere.
3. Functional Connectivity of the Medial Prefrontal Cortex and Ventral Striatum—change from baseline to 4 weeks. Measured by correlation of region activity over MRI time series data, averaged for left and right hemisphere.
4. Kirby Delay Discounting Questionnaire, 27 Item

5. Number of Days of Methamphetamine Use in the Past Week
6. Urine Drug Screen Positive for Stimulant
7. Brief Substance Craving Scale
8. Brief Addiction Monitor—Use Subscale
9. Brief Addiction Monitor—Risk Factors Subscale
10. Brief Addiction Monitor—Protective Factors Subscale
11. Brief Addiction Monitor—Satisfaction with Progress Toward Achieving Recovery Goals (question 17)
12. Quality of Life Enjoyment and Satisfaction Questionnaire—Short Form
13. Patient Health Questionnaire--8 Item Scale
14. Generalized Anxiety Disorder 7-item Scale
15. Assessment of Recovery Capital
16. Positive and Negative Affect Scale—Positive Affect Score

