17. Positive and Negative Affect Scale—Negative Affect Score
18. Pittsburgh Sleep Quality Index
19. Difficulties in Emotion Regulation Scale--Short Form
20. UPPS-P Impulsive Behavior Scale, 59-item Revised Version

Safety outcomes

Adverse events are reported at each TMS treatment visit, or if otherwise volunteered by subject.

Populations to be analyzed

Intention to treat: Subjects will be analyzed in the groups they were randomized to. However, only complete data will be used, and subjects were discontinued from the study if they missed more than 4 TMS treatments.

Analyses

Descriptive statistics will be examined for demographic and other variables, overall and by intervention group.

For other analyses, a fixed time will be assigned for each study visit, which approximates the time at which the visit would have occurred on a typical study schedule.

Primary outcomes

The primary analysis will compare intervention groups (DLPFC first or MPFC first) on time to discontinuation in the study and time to discontinuation of psychosocial treatment. The latter is defined as a participant indicating they are no longer in or seeking treatment. All subjects were in treatment or planning treatment at baseline, as an inclusion criterion. Time retained in the study or treatment will be described using Kaplan-Meier curves, and intervention groups will be compared using log-rank tests.

Secondary outcomes

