Most secondary outcomes will be examined using linear mixed models. These allow for estimation of within group change over time as well as between group differences in change over time. Group by continuous time interaction terms will be the primary test of hypotheses for differences between groups. For outcomes measured at only two time points (baseline and week 4), if sample size is not adequate or mixed models do not converge, changes from baseline to the second measure will be calculated. Wilcoxon-rank sum tests or t-tests comparing differences in changes from baseline to week 4 will be used to compare groups, as appropriate based on the data distribution. A generalized estimating equations model clustered on subject with a logit link, with empirical standard error estimates, will be used to analyze the outcome of positive urine drug screens for stimulants, as this is binary, and this approach does not assume a correlation structure. The primary analysis of this outcome will still use a group by continuous time interaction to examine whether the odds of a positive urine drug screen decreases over time in each group, and whether any reduction over time differs between groups.

Missing data

As this is a pilot study with a small sample size, and dropout is expected, analyses will use all available data as feasible for randomized subjects who received at least one treatment, irrespective of the number of data points collected. For changes in functional connectivity as measured by MRI, only subjects with both baseline and 4-week assessments will be included. No imputation of data will be performed.

References

1. Governor's Office of Drug Control Policy. News Release - Iowa Drug Control Report: Life-Changing Progress Amid Evolving Threats.
<https://odcp.iowa.gov/news-release-iowa-drug-control-report-life-changing-progress-amid-evolving-threats>. Published 2019. Updated November 13, 2019. Accessed December 13, 2019, 2019.
2. Iowa Department of Public Health. Substance Abuse Brief, December 2018, Issue 7.
https://idph.iowa.gov/Portals/1/userfiles/133/IASubAbuseBriefNewsletterDec2018_Final.pdf. Published 2018. Accessed December 13, 2019, 2019.

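### The SAP states two conflicting data rules, and study retention 'from baseline' is analysed in a set that starts only at the first TMS session

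*Combined protocol and SAP*

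**What the plan says.** Two sections of the SAP set the data rule. Populations to be analyzed keeps subjects in their randomized groups and then adds: "However, only complete data will be used, and subjects were discontinued from the study if they missed more than 4 TMS treatments". Missing data says that "analyses will use all available data as feasible for randomized subjects who received at least one treatment, irrespective of the number of data points collected". It rules out imputation and makes one exception, for MRI connectivity change, where "only subjects with both baseline and 4-week assessments will be included". The heading of the secondary outcomes list adds that these "used all available data points as specified in figure 2".

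On retention, Sample Size Justification states: "The overarching goal is to evaluate the ability to recruit and retain subjects". The first primary outcome is "Retention in the Study: Measured from Baseline to 12 weeks". It is analysed as time to discontinuation, with Kaplan-Meier curves and a log-rank test between the two order groups. Under Randomization, "The subject is assigned to a group at the first TMS treatment visit". Under Study Procedures, after the assessment visit that precedes TMS: "Within a week of this visit, the subject will begin TMS treatment".

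**The concern.** The two data rules select different subjects. The Populations sentence has no limit on it, so an analyst who follows it could drop anyone with a missing assessment. The protocol expects such subjects: Minimizing emotional risks lets some continue without completing every assessment. The Missing data section keeps them.

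The retention question concerns the denominator. A pilot that sets out to show it can recruit and keep people with methamphetamine use disorder needs to count those who complete a 3-4 hour baseline visit and do not return for stimulation. If the clock starts at that visit but the analysed set starts at the first treatment, those losses appear in no planned analysis, and the estimate is biased in a known direction. A later trial would be planned on that estimate.

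**Working it through.** **Figures in the plan.** Sessions: 2 × 5 + 2 × 3 = 16, which agrees with the Intervention section. Missing more than 4 therefore means attending fewer than 12 of 16 (75%). The sample size of about 20 cannot be reproduced, because no alpha, power, effect size, SD or dropout rate is given. It is not disputed here.

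**Data rule, side by side.**
- Populations to be analyzed: complete data only, no outcome named.
- Missing data: all observed data from treated subjects, any number of data points, no imputation, paired scans for MRI only.
- If the first rule governed everything, the separate MRI pairing rule would be redundant. That points to the second rule as the intended one, with 'complete' perhaps meaning 'not imputed'. The text does not say so.
- The Missing data rule also requires one treatment received. That makes the set modified intention-to-treat, whereas the SAP labels it intention-to-treat.

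**Who enters the retention analysis.** A subject needs a group, assigned at the first TMS visit, and at least one treatment. Between the baseline visit and that point lie 0 to 7 days. An eligible subject lost in that interval has neither. A subject who is assigned but never treated is also excluded. Subjects found ineligible at the first visit are screen failures and rightly do not count.

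**What baseline means.** The documents do not define it as a time zero.
- For the pre-TMS visit: Study Procedures calls it the baseline visit, and the baseline scans are done there.
- For the first TMS day: Study Procedures counts the 8- and 12-week follow-ups from the start of treatment.
- The 18-day window of the other primary outcome does not settle it. With day 0 on the first TMS Monday of Figure 1, day 18 is the Friday of TMS week 3. With day 0 a week earlier, it is the Friday of TMS week 2. Both are assessment days.

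**Direction and illustration (assumed counts).** Let N eligible subjects complete baseline, k be lost before TMS and R be retained at week 12. Retention from baseline is R/N; the analysed set gives R/(N − k), which is larger whenever k and R exceed 0. With N = 20 and R = 12:
- k = 0: 12/20 = 60.0%
- k = 1: 12/19 = 63.2%
- k = 2: 12/18 = 66.7%
- k = 3: 12/17 = 70.6%
- k = 4: 12/16 = 75.0%

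If the 20 are instead all treated and 14 are retained, the analysed figure is 14/20 = 70.0%. Adding 2, 4 or 6 pre-TMS losses gives 14/22 = 63.6%, 14/24 = 58.3% or 14/26 = 53.8% from baseline.

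**Order comparison.** Subjects lost before assignment have no group and cannot enter the log-rank test, so it does not change.

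**The case against.** The section headed Missing data is where an analyst would look, and its rule is clear. The complete-data clause may be only loose wording. The note on the secondary outcomes adds little, since it can simply mean the scheduled time points. Baseline may have meant the first TMS day; TMS could start on the day of the first visit, and the gap is a week at most. No retention threshold is set, so no prespecified decision turns on the figure. All this is fair. It limits the size of the point, but it does not reconcile the two sentences or define time zero.

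A reader might infer three stronger things that the documents do not support.
- **That the trial plans a completers analysis with heavy loss of data.** The Missing data section points the other way. A calculation requiring all six post-baseline visits would apply to only two of the 20 secondary outcomes, days of use and the craving scale; the others have four, three or one in Figure 2.
- **That retention swings widely with the coding of subjects removed for missed sessions.** With 4 removals and 4 withdrawals among 20, retention is 12/20 = 60% if removals are events. If they are censored it is 12/16 = 75% when all removals come first, or 16/20 = 80% when all come last. But the SAP uses the same term, discontinuation, for the removal and for the endpoint, so removal reads naturally as an event. The contrast needs the less natural reading.
- **That many subjects would be removed by the attendance rule.** The documents give no rate of missed or withheld sessions, so any expected count is invented.

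**Conclusion.** Two points stand. The data rules contradict each other as written; the Missing data rule is probably intended, and the other sentence, taken literally, is a completers analysis. And if baseline is the pre-TMS visit, the primary retention figure leaves out eligible subjects lost before TMS and can only be too high as an estimate of retention from baseline. The direction is certain on that reading. The size is unknown: the 60% to 63-75% range rests on assumed counts and is not a forecast. If baseline is the first TMS day, the figure is not biased against its own definition, but pre-TMS losses still go unreported in a study of recruitment and retention.

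The handling of rule-based removals and of withheld sessions is missing detail that calls for minor clarification only. The point is worth correcting because the repair is cheap and concerns a primary feasibility outcome.

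**What to change.** 1. Delete the complete-data clause from Populations to be analyzed and keep the Missing data rule. Call the set modified intention-to-treat and report the number randomized but untreated.
2. Define time zero for both primary outcomes. Report overall study retention among eligible subjects who completed the baseline visit, with pre-TMS losses as events and screen failures counted separately. Keep randomized subjects for the order comparison.
3. As minor clarifications, state that removal under the attendance rule is a study-discontinuation event, and report it separately from participant withdrawal where the reason is recorded. State how it is handled for psychosocial retention, where the event depends on the participant's own report. Reconcile the attendance rule in the SAP with the withheld sessions in Study Procedures and in Minimizing the risks of TMS, which do not say whether a withheld session counts as missed. No clinical rule is proposed here.

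Cost: one clause deleted, a few sentences added and one retention table; no new visits or assessments. Reported retention may be lower. Reasons for discontinuation may need to be recorded, since Figure 2 has no entry for them.

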symptoms, anxiety symptoms, and withdrawal symptoms during TBS treatment. Evaluate the level of continued use of methamphetamine during TBS treatment.

This pilot study will focus on our ability to engage patients with methamphetamine use disorder in TBS treatment and to complete a series of assessments over three months. We expect to observe reductions in cravings, withdrawal and related symptoms over time, and changes in anterior cingulate cortex functional connectivity from baseline to 4 weeks. Differences between subjects randomized to receive stimulation at the DLPFC and MPFC will be examined.

Significance

Methamphetamine (MA) use can cause many serious adverse health consequences and is of particular concern in Iowa. In the 2017 Treatment Episode Data Set (TEDS), 27.7% of substance use disorder treatment admissions involved MA as the primary substance, representing 7,641 admissions, second only to alcohol. Overdose deaths in Iowa involving MA roughly doubled to 91 from 2013 to 2018.(1,2) Treatment for MA use disorder (MAUD) is primarily psychosocial, rates of treatment induction and retention are poor, and relapse rates are high.(3) There is a pressing need to identify effective interventions that enhance psychosocial treatments. rTMS is a non-invasive brain stimulation technique that effectively treats major depressive disorder and is considered safe, well-tolerated, and potent. rTMS has increasingly been studied to treat addiction.(4-7) The dorsolateral prefrontal cortex (DLPFC), a brain region implicated in regulatory processes related to emotion, motivation, and craving, is a common target for rTMS. DLPFC stimulation using high frequency rTMS has reduced craving in many studies of addictive disorders, including cocaine and MA use disorders.(4) Despite these encouraging findings, no trials have reported on the efficacy for reducing MA use or preventing relapse. iTBS is a type of TMS has been studied in depression and shown to have equivalent efficacy to rTMS, and treatments can be delivered much more quickly than traditional rTMS.(8) In contrast to high-frequency rTMS and intermittent theta burst stimulation, which increase neuronal excitability, continuous theta burst stimulation (cTBS) decreases excitability. cTBS targeting the MPFC during drug cue activation reduced craving and related brain

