The study intervention is open-label dual-target theta burst stimulation delivered in sequential fashion to the DLPFC and the MPFC. The order of treatments is determined by the randomization scheme, but the treatments are otherwise identical. Treatment targeting will occur at the Beam F3 and FP1 scalp regions as defined by the 10-20 EEG system. A Magventure MagPro X100 figure-8 coil with theta burst capabilities will be used to deliver the stimulus, including intermittent theta burst stimulation to the DLPFC (2 seconds of 50-Hz triplets delivered at 5 Hz, 8 seconds intertrain interval, 600 total pulses) and continuous theta burst to the MPFC (continuous 50-Hz stimulation triplets, 600 pulses). Stimulation will be delivered at 110% of the resting motor threshold, as determined by the stimulation threshold at which single-pulse TMS stimulation over the motor cortex hand knob region can elicit visible finger movement on 3 of 5 trials, with stimulation dose adjustment for distance from target to coil as needed. Treatment sessions will consist of a single treatment protocol at each stimulation site. Sessions will occur 5 times per week for the first 2 weeks, followed by 3 sessions per week for an additional 2 weeks (16 treatment sessions total).

Study Procedures

This study lasts for a total of 12-13 weeks, and involves 19 visits. Although visits vary from 15 minutes to 5 hours, they average 45-50 minutes. The first week involves a baseline visit that will take 3-4 hours. If the subject elects to participate in the optional EEG and timing task, this will add about an hour to their first visit. Subjects will receive 4 weeks of TMS treatments, and each treatment should take about 15 minutes. The first two weeks of treatment involve 5 visits per week

where the subject receives TMS. The third and fourth weeks of treatment involve 3 visits per week where the subject receives TMS. Additional assessments are done on the last treatment day of each treatment week. These visits, including treatment time, will take about 30 minutes after the first and third weeks of treatment, 45-60 minutes after the second week of treatment, and 3-4 hours after the fourth week of treatment. If the subject elects to participate in the optional EEG and timing task, this will add about an hour to their visit after the fourth week of treatment. Follow-up phone calls lasting 45-60 minutes will take place 4 weeks and 8 weeks after the end of TMS treatment (week 9 and week 13 of the study).

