TMS treatment using theta burst stimulation will be provided 5 days in the first week, five days in the second week, and three times per week in weeks 3 and 4. The start day will be somewhat flexible. Subjects will participate in 5 treatment sessions in each of the first two 7-day periods, and three treatment sessions in each of the third and fourth 7-day periods (treatment weeks). Theta burst stimulation can be completed in as little as 3 minutes per treatment (two sites), so these visits should take roughly 15-20 minutes total when once-weekly additional assessments are not being completed. We will measure blood pressure and pulse prior to each treatment. If systolic blood pressure exceeds 160 mmHg, diastolic blood pressure exceeds 100 mmHg, or pulse exceeds 110 beats per minute, then we will confirm this with a second measurement. If it is confirmed by a second measurement, then the treatment will be withheld, and a clinician contacted to assess the patient. Before each treatment, we will also ask the subject when they last used methamphetamine. Treatment may be withheld if it is too recent to minimize risk of adverse effects, particularly seizure. Participants will be asked to report craving using a single question before and after each treatment. Participants will only be asked to report any adverse event experiences at these visits.

On the last day of TMS in each treatment week when TMS is administered, the subject will be asked to complete additional assessments. At 1 week, 2 weeks, and 3 weeks, these will involve completion of surveys. At weeks 1 and 3 only the Brief Substance Craving Scale will be administered, while additional survey instruments will be administered after week 2. These visits will also involve reporting of the number of days in the last week in which they used methamphetamine as well as whether they remain engaged in a psychosocial treatment and what treatments (partial hospitalization, intensive outpatient, outpatient medical, outpatient psychotherapy, group therapy, other, none). If they were engaged in partial hospitalization or intensive outpatient treatment, we will ask whether they completed the planned course of treatment or stopped early.

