After the last treatment in week 4, the subject will be asked to again complete all assessment instruments, provide information on substance use in the last week, complete the psychological tests, submit a urine drug screen (if there is not a recent result on file in their EHR), and complete fMRI imaging. If the subject elects

to participate in the optional EEG and timing task, this will add about an hour to this visit. If they elect to participate in this optional EEG and task, we will be adhering electroencephalogram (EEG) leads to their scalp and then have them perform 2 blocks of the interval timing task where they estimate the passage of a specified (3 or 12 second) passage of time (~22min - 11 min blocks). The beginning of the trial is indicated by the presentation of either a 3 or a 12 on the computer screen which also indicates the duration of time the subject should estimate. During performance, we will collect electroencephalographic data from patients which will be analyzed offline.

TMS treatment will end at this time. We will then plan follow-up visits at 8 weeks and 12 weeks after the start of treatment, which can be completed by phone/online or in person base on the subject's preference. At these visits subjects will complete the survey-based assessments. They will also be asked about the number of days of methamphetamine use in the last week and their current psychosocial treatment modality.

An example study schedule and full list of assessments I provided below.

Figure 1: Example Study Schedule

Study Week	Monday	Tuesday	Wednesday	Thursday	Friday
1	First visit: determine eligibility to continue, questionnaires, psychological testing, urine drug screen if needed, MRI, optional EEG (3-5 hours)				
1	TMS	TMS	TMS	TMS	TMS, questionnaires, urine sample if needed (about 30 minutes)
2	TMS	TMS	TMS	TMS	TMS, questionnaires, urine sample if needed (45-60 minutes)
3	TMS		TMS		TMS, questionnaires, urine sample if needed (about 30 minutes)
4	TMS		TMS		TMS, questionnaires psychological testing, urine sample if needed, MRI, optional EEG (3-5 hours)
8	One follow-up visit or phone call to complete questionnaires (45-60 minutes)				
12	One follow-up visit or phone call to complete questionnaires (45-60 minutes)				

Figure 2: Schedule of study assessments by visit

Measure	Time to complete (minutes)	First Visit	Last TMS day week 1	Last TMS day week 2	Last TMS day week 3	Last TMS day week 4	Week 8	Week 12

Interview Questions								

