TMS will be administered by combining an FDA-approved protocol and a protocol that has been previously studied with no notable differences in adverse effects, and will be overseen by a psychiatrist in the clinical TMS service in the standard fashion.

We will measure blood pressure and pulse prior to each treatment. If systolic blood pressure exceeds 160 mmHg, diastolic blood pressure exceeds 100 mmHg, or pulse exceeds 110 beats per minute, then we will confirm this with a second measurement. If it is confirmed by a second measurement then the treatment will be withheld and a clinician contacted to assess the subject and their potential need for acute medical care. We will also ask the person when they last used methamphetamine, and withhold treatment if we believe they may still be intoxicated with methamphetamine.

Minimizing the risks of MRI:

To reduce the risk of a metal object flying through the air and hitting the subject, technologist or nearby person, we require that all people involved with the study remove all metal from their clothing, pockets and body prior to entering the scan room. No metal objects will be brought into the magnet room while the subject is inside the room. In addition, the door to the room remains closed throughout the entire study so that no one accidentally takes a ferrous metal object into the scan room. We also have a ferromagnetic detector for the research suite. The metal detector will work in tandem with our MRI screening sheet to ensure no metal is accidentally overlooked and taken into the scan room.

-Subjects will be given either ear plugs or headphones to reduce the risk of hearing damage.

-In the event that an abnormal finding is suspected, a radiologist trained in reading the examination will be consulted. If it is felt that the subject needs to be notified in order to seek out further medical advice, a physician will then contact the subject to discuss the issue.

-Exposure to magnetic fields and radiofrequency fields will be kept to a minimum by setting a cutoff time of any study of 90 minutes in the magnet.

-Subjects will be given a squeeze ball while in the MRI scanner to alert the investigators to stop the study.

Minimizing emotional risks:

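### Missing more than 4 TMS sessions ends study follow-up as well as TMS, so outcome data may be lost in a use-related way and rule-forced removals enter the 12-week retention outcome

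*Combined protocol and SAP*

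**What the plan says.** In the SAP, Populations to be analyzed states that "subjects were discontinued from the study if they missed more than 4 TMS treatments". The wording concerns the study, not only the stimulation. The same sentence limits analysis to complete data, whereas Missing data says that everything available will be used for randomized subjects with at least one treatment. No imputation is planned.

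Study Procedures has staff ask about last methamphetamine use before each session: "Treatment may be withheld if it is too recent to minimize risk of adverse effects, particularly seizure". It also covers confirmed high blood pressure or pulse: "If it is confirmed by a second measurement, then the treatment will be withheld, and a clinician contacted to assess the patient". Under Minimizing the risks of TMS, staff are to "withhold treatment if we believe they may still be intoxicated with methamphetamine". No section says whether a withheld session counts as missed or can be made up.

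Follow-up at weeks 8 and 12 consists of surveys and self-reported use, "which can be completed by phone/online or in person base on the subject's preference". The first primary outcome is "Retention in the Study: Measured from Baseline to 12 weeks". A secondary objective is "Evaluate the level of continued use of methamphetamine during TBS treatment", and the Overview plans three months of monitoring.

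**The concern.** Stopping TMS and leaving the study are different events, and the rule merges them. A participant who misses a fifth session but would answer every later survey gives no further data.

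If people who keep using are the likelier to miss sessions, whether an outcome is observed depends on the outcome itself. Sample Size Justification makes the apparent improvement in symptoms and use a goal of the pilot, and Potential Benefits to Society treats improvement as part of the case for a randomized trial. A distorted picture of change would carry into that decision.

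The primary outcome is affected as well. Study retention to 12 weeks becomes in part a restatement of TMS attendance in the first four weeks.

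**Working it through.** **Schedule.** Sessions are 5 + 5 + 3 + 3 = 16, which matches the Intervention section. More than 4 missed means the fifth, and 5/16 = 31%.

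**What is lost.** Removal ends the remaining weekly assessments, the week-4 battery and the week-8 and week-12 contacts. The only section on absent participants, Procedures for contacting subjects lost to follow-up, is for people who cannot be reached.

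**How selective the rule can be.** The documents give no miss rate, so the per-session probability p is assumed. With X ~ Binomial(16, p), the chance of removal is P(X ≥ 5):

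| p | Chance of removal |
|---|---|
| 0.05 | 0.1% |
| 0.10 | 1.7% |
| 0.20 | 20% |
| 0.30 | 55% |
| 0.40 | 83% |

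As an illustration, take the planned 20 as 10 people at p = 0.10 and 10 at p = 0.30. Expected removals are 10 × 0.017 = 0.17 and 10 × 0.55 = 5.5. A moderate link between use and attendance becomes strong selection.

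**Direction of bias.** Simulations used a true mean change of about zero and stopped observation at the fifth missed session. Each scenario had 1,500 to 3,000 simulated participants, to isolate bias from the noise of a small trial. Miss probabilities and use patterns are assumptions. The urine-screen model used GEE with an independence working correlation, because the SAP names none.

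- *Missing unrelated to use* (p = 0.10 or 0.20 for all): no drift beyond noise.
- *Stable use, p rising from 0.05 (no use) to 0.30 (daily use)*: 17% removed (7% of lower users, 27% of higher users). Raw mean use at week 12 was 0.22 days/week lower than at baseline. The urine-screen odds ratio over 4 weeks was 0.81 (truth 1). The mixed-model change over 12 weeks was -0.01 days/week.
- *Stable use, p rising to 0.60*: 59% removed (38% against 81%). Raw change -1.00, odds ratio 0.31, mixed model -0.03.
- *Diverging individual trends*: mixed model with random intercept only, -0.04 to -0.22; with random slopes, +0.08 to +0.13, with some convergence warnings.
- *Use switching between 1 and 5 days/week, p = 0.05 when low and 0.20 to 0.60 when high*: with 5% switching per week, odds ratios ran from 0.82 down to 0.06; with 15%, from 0.94 down to 0.16. The mixed model moved the other way, +0.03 to +1.23, because retained low users drift back up. Raw week-12 means fell by 0.13 to 0.72 with 5% switching, but stayed within about 0.05 of the truth with 15%.
- *Within-person change to week 12 among those never removed*, where missing depended on use: -0.16 to +1.17 days/week. Restricting to complete data does not settle the direction.

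**Effect of continued follow-up**, tested only in the switching scenarios: odds ratio 0.98 to 1.09, and mixed-model change -0.17 to +0.10 days/week, which is simulation noise.

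**Retention.** The SAP analyses time to discontinuation of the study and does not distinguish removal under the rule from refusal or loss of contact. On the natural reading both are the same event.

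**The case against.** The best defence is the analysis model. Most secondary outcomes go to linear mixed models, which largely correct for dropout predicted by observed use, and under stable use they were nearly unbiased. That stands, so a reader who infers that all use and symptom outcomes drift towards improvement goes too far. The drift is supported for the urine-screen GEE and for raw means when use is fairly stable. For mixed-model outcomes the sign is open, and symptom scales were not examined. The defence also depends on the all-available-data statement prevailing over the complete-data one.

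A second defence is that the objective concerns use during treatment, so off-treatment data answer another question. This has some force, but weeks 8 and 12 are off treatment for everyone and are planned anyway. Counting non-adherence as non-retention is defensible in a feasibility pilot, provided that the two are reported apart.

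Other stronger readings are not supported:

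- *Withheld sessions lead to removal.* The documents do not say that they count as missed. The link is a reasonable inference and no more.
- *Removal can occur in week 1.* That requires missing all five sessions. Group assignment happens at the first TMS visit, and the analysis set needs at least one treatment. An analysed person can have missed at most 4 in week 1, so the rule cannot apply before week 2.
- *The rule breaches intention to treat.* The SAP defines this as analysis in the randomized group. Data not collected are missing data.
- *It contradicts the allowance for incomplete assessments.* That text, under Minimizing emotional risks, concerns distress during testing, not missed TMS.
- *A percentage bias can be stated.* Without miss rates or use levels, any such figure would be invented.

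**Conclusion.** The concern holds in a limited form, and the plan should be changed. As written, the fifth missed session ends outcome collection when most of the remaining assessments need no TMS. The loss is plausibly related to use, and no sensitivity analysis addresses it. The urine-screen analysis and raw summaries may look too favourable. Mixed-model outcomes may be biased either way. The amount cannot be derived from the documents and depends on how strongly missed sessions follow use; if they are unrelated, the trend bias disappears. The mixing of rule-forced and voluntary exits in a primary outcome needs no such assumption beyond the rule being applied. When TMS should be withheld or stopped is a clinical matter and is not judged here.

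**What to change.** - Leave the TMS attendance rule unchanged, but state that exceeding it ends TMS only. Remaining scheduled survey and use assessments continue unless consent is withdrawn, by phone or online where possible. Urine screens through week 4 need an in-person option where feasible, since remote contact cannot replace them.
- Report TMS discontinuation and study discontinuation as separate outcomes, with reasons.
- Record missed and withheld sessions separately, and state which count towards the limit.
- Reconcile Populations to be analyzed with Missing data in favour of all available data.
- Add a sensitivity analysis for informative dropout, for example counting missing urine screens as positive.

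The SAP words the rule in the past tense, so it may already have been applied. If follow-up is over, report removals by reason, separate rule-forced removals from other exits in the retention analysis, and run the sensitivity analysis.

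The cost is revised wording, a few more contacts of a kind already planned, some off-treatment data, and possibly less favourable use figures.
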